## 3 Population

### 3.1 Intention-to-treat Analysis

An intention-to-treat analysis will be the primary method for analysing and summarising the trial data. The intention-to-treat population is defined as all randomised patients, regardless of eligibility, withdrawal, compliance with the protocol, loss to follow-up or actual treatment received. Only patients who have withdrawn their consent for their data to be used in the study, or for whom written informed consent has not been received, will be excluded in this population. These patients will be analysed and summarised according to the intervention they were randomised to receive.

If more than 5% tests or trial conduct constitute a major protocol violation such as cross-over to the other arm or cancelling surgeries, the Complier Average Casual Effect analysis will be considered.

### 3.2 Quality of life populations

A separate quality of life population will be formed for the analysis of each questionnaire (SF36). Each population will comprise all patients who return an analysable baseline questionnaire, regardless of subsequent questionnaire return: patients without analysable baseline questionnaires will be excluded from the analysis, regardless of subsequent questionnaire return.

### 3.3 Safety Population

All patients will be included in the safety population if they underwent one of the two procedures. Patients will be included in the arm corresponding to the intervention received. If no intervention was received, then the patient will be summarised separately from the other intervention groups.

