### 2.2 Secondary outcomes

Clinical endpoints of SR at 24 months after surgery, overall survival and stroke-free survival, incidence of anticoagulant-related haemorrhage.

Health-related QoL measured by the EuroQoL, SF-36 and NYHA.

Resource use and cost-effectiveness of the adjunct maze procedure.

Anticoagulant and antiarrhythmic drug usage.

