## 5.9 Safety Analysis

A listing of total number of adverse events in each category as well as the deaths from any cause will be presented, and summarised by treatment group, corresponding to the intervention received. Events will be summarised according to whether they meet the

criteria of Serious Adverse Events, and whether they are thought to be related to the procedure.

Adverse Events are not planned to be categorised. However, a number of pre-specified Adverse Event categories have been specified.

Health Economic Analysis will be performed by the Health Economic Analysis team. A separate analysis plan has been written, and should be referred to for a description of the planned analyses.

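### The adverse event and death tables are grouped only by intervention received; tables by randomised group should stand beside them, and an incomplete ablation needs a classification rule

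*SAP*

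**What the plan says.** Section 3.3 defines who is in the safety population ("All patients will be included in the safety population if they underwent one of the two procedures") and where each patient is placed ("Patients will be included in the arm corresponding to the intervention received"). Patients who had neither procedure are kept outside both arms: "If no intervention was received, then the patient will be summarised separately from the other intervention groups".

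Section 5.9 uses the same grouping for its output. "A listing of total number of adverse events in each category as well as the deaths from any cause will be presented", and these are "summarised by treatment group, corresponding to the intervention received". Seriousness and relatedness to the procedure are further breakdowns of the same table. No test or interval is planned.

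Three other places bear on this:

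- Section 3.1 sets the general rule: "An intention-to-treat analysis will be the primary method for analysing and summarising the trial data". It also foresees departures from allocation: "If more than 5% tests or trial conduct constitute a major protocol violation such as cross-over to the other arm or cancelling surgeries", a complier average causal effect analysis will be considered.
- Section 4.2 has patients registered and randomised once baseline measurements are complete on the day of admission, so before surgery.
- Section 2.2 lists as secondary outcomes "overall survival and stroke-free survival, incidence of anticoagulant-related haemorrhage". Section 5 describes no analysis for any of these.

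**The concern.** Whether an allocated ablation is carried out is settled after randomisation and can depend on the patient's state in theatre. Under 3.3 and 5.9, a Routine+Maze patient operated on without ablation becomes a Routine patient in the safety tables, together with any later serious event or death. A patient whose operation is cancelled leaves both arms.

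If the patients who miss their ablation are at higher risk than the rest, this takes events out of the maze group and adds them to the control group. The summary then favours the procedure under test, and no table by randomised group is planned against which a reader could check it. The SAP accepts that cross-over may occur, yet sections 3.3 and 5.9 make no provision for it beyond reclassifying the patient.

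A related gap is that 3.3 does not say what counts as received when an ablation is started and then stopped. If such patients were classed as Routine, harm from the attempt would be counted against control.

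**Working it through.** **What is and is not tabulated by randomised group**

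| Outcome | Where | Grouping |
|---|---|---|
| Adverse events, serious adverse events | 5.9 | Intervention received only |
| All-cause death, as a mortality table | 5.9 | Intervention received only |
| Death, as zero utility within the QALY | 2.3, 5.4 | Randomised group, under the 3.1 default |
| Overall and stroke-free survival | 2.2 | 3.1 default, but no analysis written |
| Stroke within 12 months | 5.8 | Treatment group, all trial patients as denominator |

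The SAP states no figure to reproduce here. The size can only be illustrated.

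**Inputs**

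- 200 per arm: SAP 1.4.1.
- 5% of the maze arm not ablated: borrowed from the trigger in 3.1, which pools all major violations and is not a forecast of cross-over. 10% is an assumption.
- Control mortality 6% (12 deaths of 200): assumption.
- Death risk in non-ablated maze-arm patients 12% to 25%: assumption.
- Cross-over only from maze to routine: assumption.

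**Formula.** With *D*m and *D*c deaths by randomised arm, *k* patients reclassified and risk *p* among them, the as-received ratio is

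[(*D*m − *kp*)/(200 − *k*)] ÷ [(*D*c + *kp*)/(200 + *k*)].

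**True ratio 1.5 (18 v 12 deaths)**

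| Not ablated | Risk in them | Maze as received | Routine as received | Ratio |
|---|---|---|---|---|
| 5% (*k* = 10) | 12% | 16.8/190 = 8.84% | 13.2/210 = 6.29% | 1.41 |
| 5% | 25% | 15.5/190 = 8.16% | 14.5/210 = 6.90% | 1.18 |
| 10% (*k* = 20) | 12% | 15.6/180 = 8.67% | 14.4/220 = 6.55% | 1.32 |
| 10% | 25% | 13/180 = 7.22% | 17/220 = 7.73% | 0.93 |

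**True ratio 1.0 (12 v 12 deaths)**

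- 5% not ablated: 10.8/190 v 13.2/210 = 0.90 (12% risk); 9.5/190 v 14.5/210 = 0.72 (25% risk).
- 10% not ablated: 9.6/180 v 14.4/220 = 0.81 (12% risk); 7/180 v 17/220 = 0.50 (25% risk).

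**No link between omission and risk.** With a true ratio of 1.0 and 6% risk in the reclassified patients, 11.4/190 v 12.6/210 is 6.0% v 6.0%, a ratio of 1.00. No bias arises.

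**Check on the difference scale, with other assumed risks.** Take control 5%, completed maze 8%, and 5% of the maze arm not ablated.

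- Non-ablated risk 15%: as randomised 0.95 × 8 + 0.05 × 15 − 5 = +3.35 points; as received 8 − (10 + 1.5)/210 = 8 − 5.48 = +2.52.
- Non-ablated risk 30%: as randomised 7.6 + 1.5 − 5 = +4.10; as received 8 − 13/210 = 8 − 6.19 = +1.81.
- Non-ablated risk 5% (no excess over control): as randomised 7.6 + 0.25 − 5 = +2.85; as received 8 − 10.5/210 = +3.00.

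The direction is the same on both scales, and the effect disappears or slightly reverses when the reclassified patients carry no excess risk.

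**The case against.** Grouping safety data by treatment received is common practice and has a sound reason: it attributes exposure-related harm to those exposed. A comparison by randomised group has its own weakness, since events in patients never ablated or never operated on can dilute a true harm of ablation. This stands. It is why the as-received tables should stay and why which set comes first is a matter of judgement.

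Deaths are not wholly lost to the randomised comparison. They lower the QALY endpoint under intention to treat, survival is a listed outcome, and stroke is tested over all trial patients. This also stands, but a utility area is not a mortality comparison, the survival outcomes have no written analysis, and stroke is one event type within 12 months.

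Nothing in the SAP says that cross-over will be frequent, mainly one-way or driven by prognosis. Section 1.1.1 describes device ablation as generally safe and adding little to the operation. Cancelled patients stay visible in their separate summary. Section 3.1 does not confine the complier analysis to efficacy. All of this is fair and limits the claim to a conditional one.

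A reader might also infer that abandoned ablations are moved to control. The SAP does not say so. Section 3.3 leaves the case undefined, and the lesion-completeness analysis in 5.5 keeps a lowest category of 0 to 4 within Routine+Maze.

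**Conclusion.** The point holds as a gap in the planned tables. For adverse events, serious adverse events and the one mortality summary specified, the only grouping written is by intervention received, so that summary loses the protection of randomisation. Any resulting bias favours the maze procedure if omission of ablation is linked to higher risk.

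The size cannot be derived from the SAP. Under the stated assumptions, a true ratio of 1.5 would appear as 1.41 to 1.18 with 5% not ablated and 1.32 to 0.93 with 10%. At the lower assumed risk the excess remains plainly visible. Only the extreme corner removes it, and the null-case ratio of 0.50 requires 5 of 12 maze-arm deaths to fall in 20 patients (25% against 7/180 = 3.9%).

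A reader might infer that the plan hides harm from the procedure, or that deaths are examined only as treated. The document supports neither. The first depends on an unstated pattern of cross-over, and the second overlooks the intention-to-treat QALY endpoint. This is a cheap and worthwhile addition rather than an error in the choice of a safety population.

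**What to change.** In 5.9, keep the as-received tables and add beside them a summary by randomised group. It should cover all randomised patients with consent, including those whose surgery was cancelled. Give the number of patients with at least one adverse event, with at least one serious adverse event, and who died by 24 months, with differences and 95% confidence intervals by the method for two independent proportions in 5.1. List every patient who crossed over, with the outcome.

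In 3.3, state that for analysis an ablation started but not completed counts as maze received.

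The cost is SAP wording and one extra set of tables from data already collected. Cross-over slightly dilutes the randomised comparison, and the retained as-received tables cover that.

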## 4 Data Collection

### 4.1 Methods

The data is collected on to a web-based system designed and coordinated by the Data Scan and Quality Officer at Papworth Hospital. The Clinical Research Nurse (CRN) at each centre enters the data directly on to the database. Surgical data will be recorded by a designated member of the surgical team either directly or via a paper form. All paper data collection forms are returned to the R&D Unit at Papworth. The Trial Coordinator (TC) are responsible for data monitoring and quality control. The whole process is overseen by the Trial Manager situated in the co-ordinating centre at Papworth Hospital.

### 4.2 Baseline data collection

We adhere to the ACC/AHA/ECS 2006 Guidelines which recommend that the initial patient description includes demographics, type and duration of AF and the planned cardiac procedure.

The first 4-day ECG recording starts after the patient attends the preadmission clinic and has consented to participate. All other baseline measurements are recorded on the day of admission for surgery. Once these measurements have been taken, the patient is registered with the co-ordinating centre's R&D unit and randomised as described in Section 1.5.

### 4.3 Data collection during and after surgery

Data collection is based on the recommendations of Shemin et al.[13] and includes procedural details-including the lesion set in the experimental group. Data collected after surgery includes: mortality, stroke/thromboembolic events, medications, EuroQoL, health-related quality of life, cardioversion plan if appropriate, 4-day ECG recordings, resource use, adverse events.

Data are collected during surgery, at discharge, 6 weeks after surgery (at a routine service visit), at 6, 12 and 24 months after surgery during out-patient research visits and annually thereafter by telephone follow-up.

### 4.4 Analysis of ECG recordings

All 4 day continuous ECG recordings will be analysed centrally at Papworth Hospital. Participating centres forward the SD cards from the ECG recorders to Papworth Hospital. Analysis using the proprietary automated software package, together with

manual checking of the recording in its entirety, will be done. Total time spent in sinus rhythm and in AF (AF burden) during the 4 day recording will be calculated, with only those episodes of AF lasting greater than 60 seconds duration included in the analysis. Episodes of atrial flutter will be noted and included in the AF burden.

Occurrences of Atrial Flutter or Atrial Tachycardia (“Organised Atrial Arrhythmia”) in patients experiencing AF and Junctional Rhythm in patients reportedly in Sinus Rhythm will be reported.

#### 4.5 ONS tracking

All patients enrolled in this trial (with their consent) are registered with the Office of National Statistics (ONS) Tracking System to allow long term follow up of survival. ONS tracking data is not expected to form part of the primary analysis of outcomes up to 24 months. Instead, this will be used to follow-up patients over a longer period if longer-term follow-up analyses are required.

#### 4.6 Data validation

Data management will focus on the data associated with the consenting process, participant eligibility, safety, date consistency and test outcomes and this section refers to the cleaning of these items. The Data Management Assistant (DMA)/ Trial Coordinator (TC) will carry out initial validation of the forms in accordance with the trial-specific Data Management Work Instructions. This will ensure that data is complete, consistent, and up-to-date. The Data Clarification Form (DCF) will be sent to sites to highlight missing data items and queries associated with data collected on CRFs to date. Reasons should be obtained when data is unobtainable.

The database will validate most data in line with validation rules and highlight any issues that need further investigation i.e. with the site. Manual checks on all entered data will be performed prior to the validations being implemented. Data items collected relating to the safety and rights of individual patients are to be highlighted via priority validations and dealt with as a data management priority. Periodic batch validation will also be carried out to detect any data queries that may be missed if case record forms (CRFs) are entered in an order that does not allow real time validation checks to work.

A key data items list drawn up by the Trial Statistician that will include all data items that are required for the analysis of the primary endpoint. All key data items will be checked manually for completeness and accuracy by the DMA/TC, in addition to any automatic checks raised on the database. Data automatically generated through the 24-hour randomisation system will be checked by the Trial Statistician.

The Trial Statistician will also perform checks to identify any missing or inconsistent data and liaise with the Trial-Coordinator to resolve any queries.

The data will be validated and checked using SAS in the following steps:

The data will be read into permanent SAS data sets.

A random sample of 5 patients from each SAS dataset will be checked against the data as seen on the database to ensure that the data transfer has been successful. The names and contents of the variables can be found on the annotated final database specification reports in the Statistician's Trial File.

Data checks will include:-

Eligibility checks

Sequential dates

Checks for unusual and outlying data

Inconsistency in data between forms

Checks for missing data (are there variables which are systematically missing/do specific variables have a large amount of missing data, particularly key outcome data)

Other checks as deemed appropriate

Any inconsistent data will be noted and an e-mail sent to the trial co-ordinator responsible for the study. A copy of this e-mail will be kept in the statistician's trial file. All queries will be resolved and the outcome documented.

## 5 Data analysis

It is expected that the final analysis of the data will be performed when all patients have completed 24 months of follow-up.

### 5.1 General calculations

All statistical analyses and reporting will comply with CONSORT guidelines where possible.

Confidence intervals for a single proportion shall be calculated using the Exact method. Confidence intervals for a difference between independent proportions shall be calculated using Exact intervals (Method 8 of [16]).

All percentages will be calculated using the total number of patients within the specified analysis population, percentages will be reported to 1 decimal place. All statistical tests will be 2-sided and performed at the 5% significance level. All analyses will be carried out using SAS.

For summary statistics, the number of non-missing items, the means, standard deviations, medians, upper and lower quartiles and minima and maxima will be summarised to one more decimal place than the data are collected.

### 5.2 General principles

Multivariable analyses will not be 'built' following a model-fitting strategy. Instead, all variables specified for inclusion will be added to the model, and the significance of each factor will be reported. Where one categorical variable has more than one 'factor level' then the significance of overall effect of including all factor levels will be tested, rather than those for each individual factor level. For all factor levels, suitable point and interval estimates of effect size will be presented.

If any analysis requires the use of simulation and / or re-sampling methods, the initial 'seed' value for the random number generation will be 0471346543. The same seed will be used at the start of every such analysis.

### 5.3 Baseline data and surgery data

Patient baseline data and surgery data as recorded on the baseline assessment or during surgery will be tabulated using frequencies and summary statistics by treatment group, for each randomising centre and in total, for the intention-to-treat population (and safety populations if appropriate). No statistical testing will be carried out on these data.

### 5.4 Analysis of Primary Endpoints

#### Quality-Adjusted Survival

For the final primary outcome, QALYs will be estimated from serial measurements of the EQ-5D for each patient up to 2 years using interpolation. The Health Economics analysis will be given in Section 6.

At baseline, on discharge and at 6 weeks, 6 months, 12 months and 24 months post-surgery all patients complete the EuroQol questionnaire, including the EQ-5D. The social tariff for the EQ-5D, as estimated by Dolan et al. [17] will be applied to each patient's self-reported classification in order to calculate utility values. Using actual rather than nominal times of assessment, and assuming a linear change in values between time points, patient-specific utility curves up to 24-months post randomisation will be calculated. A value of zero will be applied at the date of death for those patients who died.

The QALYs experienced by each patient to 24-months post randomization are calculated as the area under their utility curve to 24 months or time of death, whichever occurs first, where the true test dates rather than nominal test dates will be utilized in plotting the utility curve. In order to adjust for differences in baseline utilities a linear regression will be fitted to the utilities post treatment, with baseline utility and treatment group as explanatory variables. The linear regression will also include a random effect for surgeon if it is feasible to fit, and yields a positive variance component for the surgeon effect. Adjusted treatment effects will be taken from the treatment group coefficient of this regression. For patients who do not complete all EuroQoL measurements and are censored the methods of Willan and Lin[18] will be used to estimate mean QALYs and costs. The adequacy of model fit for the linear regression model at each timepoint will be assessed by examining distributions of standardised residuals, association with the predicted values, as well as identifying influential observations by referring to leverage statistics.

The differences in Quality-adjusted Survival will be presented. A confidence interval for the true difference will be formed using a non-parametric bootstrap resampling approach: [19]

A simple random sample with replacement will be drawn from the full analysis dataset of the same size as the full dataset. (ie some patients may be drawn more than once)

The difference in QALYs between the two treatment groups will be estimated for this bootstrap sample.

Steps (1) and (2) will be repeated 1000 times.

The 95% confidence interval will be formed as the interval between the 2.5% and the 97.5% percentile of the differences computed in these bootstrap samples.

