#### Clinical effectiveness measured as quality-adjusted survival over 2 years

The emphasis in cost-effectiveness studies is on estimation rather than hypothesis testing so that formal sample size calculations are less important. However, we provide a power calculation based on the effectiveness measure QALY. We could find no studies reporting comparative QALYs in similar patients undergoing ablation and cardiac surgery. From previous studies of patients undergoing angiography for suspected ischaemic heart disease[14] and patients with refractory angina[15] the standard deviation of QALYs over 12 and 18 months is at most 0.3. Over follow up of 2 years the minimum clinically important improvement is considered to be one extra month of quality-adjusted life, or 0.083 QALYs. With a sample of 200 patients per group, total 400, we would have approximately 80% power to detect a difference of 0.083 QALYs, (2-sided significance 5%). If the accepted threshold for cost effectiveness were in the range £20-30,000 per QALY and we could demonstrate a significant increase in QALYs of 0.0833, then the procedure would be cost-effective for an incremental cost of at most £2,500.

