## 1.5 Randomisation

Patients who fulfil the eligibility and have given written informed consent and have sufficient time for discussion and consideration, are randomised (in a 1:1 ratio) to one of two groups to receive either their routine cardiac surgery with no additional procedure or their routine cardiac surgery with an adjunct maze procedure.

Patient allocations are computer generated by the trial statistician and are in random permuted blocks of variable lengths, stratified by surgeon and by planned cardiac procedure (CABG, aortic valve, mitral valve, combined procedure).

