#### 5.5 Subgroup Analysis

Subgroup analysis will include those patients for whom measurements are available.

The first objective of subgroup analysis is within the whole dataset, to account for potential variation in the treatment effects between

patients with paroxysmal and non-paroxysmal AF: Paroxysmal AF vs. Persistent Chronic or longstanding AF.

individual centres (as a random effect to allow for heterogeneities in small centres

different cardiac surgical procedures

different surgeons.

different lesion sets.

The different lesion sets are to be defined as follows:

minimal LA lesion set: pulmonary vein isolation only ± LA appendage line

more extensive LA lesion set excluding mitral annulus

more extensive LA only lesion set including mitral annulus

minimal LA lesion set + RA lesion set

more extensive LA lesion set excluding mitral annulus + RA lesion set

more extensive LA lesion set including mitral annulus + RA lesion set

In the event that patients are too sparsely-distributed across the 6 categories, the categories will be combined into 4, by combining (i) with (ii) and combining (iv) with (v). If this is still too sparse to facilitate comparison, then the lesion set subgroup will be reduced to a comparison of category (vi) to all other groups.

For the Quality-Adjusted Survival Endpoint, a linear regression model will be fitted to the Area Under the Utility Curve, with baseline EQ5D score, surgeon, surgical procedure, treatment group, subgroup variable and the subgroup-by-treatment interaction variable. The treatment modifying effect will be reported with a 95% confidence interval. The Area under the utility curve will be appropriately transformed prior to performing subgroup analyses, and the results back-transformed where necessary.

For the Return to SR Endpoint, a logistic regression model will be fitted to heart rhythm at 12 months with the baseline heart rhythm, surgeon, surgical procedure, treatment group, subgroup variable of interest and its interaction term with treatment group. The odds ratio of the interaction term between treatment and subgroup variable will be reported with 95% confidence interval and p-value for the data seen, under the null hypothesis that there is no difference in the treatment effects on patients within different subgroup of interest.

The second objective is within the Routine+Maze treatment group, to account for variation in the treatment effects between

different ablation devices

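### The primary QALY analysis regresses post-treatment utilities rather than QALYs, and the SAP does not say whether the bootstrap interval belongs to the adjusted difference

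*SAP*

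**What the plan says.** All of this is in the SAP.

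- **Endpoint.** Section 5.4 (Quality-Adjusted Survival) builds a utility curve for each patient from EQ-5D at baseline, discharge, 6 weeks and 6, 12 and 24 months. QALYs are the area under that curve, stopped at 24 months or at death.
- **Adjusted effect.** The same section then states that "a linear regression will be fitted to the utilities post treatment, with baseline utility and treatment group as explanatory variables". A random surgeon effect is added if it can be fitted and its variance is positive. The adjusted effect is the treatment coefficient of this regression.
- **Model check.** "The adequacy of model fit for the linear regression model at each timepoint will be assessed".
- **Interval.** Patients are resampled with replacement from the full dataset 1000 times, and the percentile limits are taken. The step that defines the statistic reads "The difference in QALYs between the two treatment groups will be estimated for this bootstrap sample".
- **Subgroup model for the same endpoint.** Section 5.5: "a linear regression model will be fitted to the Area Under the Utility Curve, with baseline EQ5D score, surgeon, surgical procedure, treatment group", plus the subgroup and interaction terms, with the area transformed where appropriate.
- **Randomisation.** Section 1.5: allocation is "stratified by surgeon and by planned cardiac procedure". Procedure is in the return-to-SR models at 12 months (5.4) and 24 months (5.6), and in the QALY subgroup model (5.5). It is not in the primary QALY model.

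**The concern.** The primary regression, read literally, does not have the primary endpoint as its outcome. A QALY total is one number per patient and has no timepoints, so the per-timepoint model check makes it hard to read utilities as shorthand for QALYs. If the model is fitted visit by visit, there are up to five post-baseline coefficients and none is named as primary. If visits are pooled, no term for repeated measurements within a patient is given, although the SF-36 model in section 5.7 has one.

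The bootstrap is for a QALY difference, so it cannot be the interval for a utility coefficient. Nor does the text say whether it is the interval for a baseline-adjusted QALY difference. Two statisticians following section 5.4 could report different primary estimates with different intervals, and the choice could be made after the data are seen. The sample size argument in section 1.4.1 is on the QALY scale, so the reported estimate needs to be on that scale too.

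**Working it through.** **1. The plan's own figure.** Inputs from section 1.4.1: "With a sample of 200 patients per group, total 400, we would have approximately 80% power to detect a difference of 0.083 QALYs", SD at most 0.3; section 5.1: "All statistical tests will be 2-sided and performed at the 5% significance level". Standard error = 0.3 × sqrt(2/200) = 0.030. Power = Φ(0.083/0.030 − 1.96) = Φ(0.807) = 79.0%. The stated figure of about 80% reproduces. It uses an SD with no baseline adjustment.

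**2. Scale.** The target is stated in QALYs: "minimum clinically important improvement is considered to be one extra month of quality-adjusted life, or 0.083 QALYs".
- Constant utility difference over the full 2 years: 0.083/2 = 0.0415.
- Difference that starts at zero at baseline, rises linearly to 6 weeks (6/52 = 0.115 years) and is constant to 2 years: area per unit of utility = 0.115/2 + (2 − 0.115) = 1.94. The matching utility difference is 0.083/1.94 = 0.043.

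So a utility coefficient and a QALY difference differ by a factor of about 1.9 to 2.

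**3. Pooling visits does not recover the area.** By the trapezium rule at nominal times, discharge carries (6/52)/2 = 0.058 of 2 years, or 3% of the area. Twelve months carries (2 − 0.5)/2 = 0.75 of 2 years, or 37.5%. Equal weighting of five visits, an assumption because the SAP gives no weights, would give each 20%.

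**4. Adjusted against unadjusted interval.** The SAP gives no correlation r between baseline utility and QALYs, so r is assumed. Half-width = 1.96 × 0.030 × sqrt(1 − r²); width ratio = 1/sqrt(1 − r²).

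| r (assumed) | 95% half-width | Unadjusted ÷ adjusted width | Power for 0.083 |
|---|---|---|---|
| 0 (unadjusted) | 0.0588 | 1 | 79% |
| 0.3 | 0.0561 | 1.048 | 83% |
| 0.5 | 0.0509 | 1.155 | 89% |
| 0.7 | 0.0420 | 1.40 | 97% |

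**5. Leaving out procedure.** Simulation of 2000 trials: n = 400, four equal procedure strata balanced by arm, r = 0.5, true effect 0.083. The share of QALY variance due to procedure is assumed. All models adjust for baseline.

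| Variance due to procedure | Model SE without / with procedure | Coverage without / with | Power without / with |
|---|---|---|---|
| 0% | 0.0260 / 0.0260 | 94.4% / 94.3% | 89.4% / 89.4% |
| 2% | 0.0260 / 0.0256 | 95.7% / 95.3% | 89.0% / 89.6% |
| 5% | 0.0260 / 0.0251 | 95.8% / 95.4% | 89.7% / 91.2% |
| 10% | 0.0260 / 0.0242 | 96.0% / 94.8% | 90.6% / 93.0% |

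Because the strata are balanced by arm, omission does not bias the effect. At 10%, the empirical standard error is 0.0243 with or without procedure. The model standard error of 0.0260 is therefore slightly too large, and the omission is mildly conservative.

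**The case against.** The strongest defence is that the wording is loose, not the method. QALYs are a linear combination of utilities, so baseline-adjusted differences at each visit could be integrated to an adjusted QALY difference. Section 5.5 shows that the authors had a regression on the area under the curve in mind. Nothing in the SAP proposes to report a utility coefficient as QALYs, so the factor of about 2 is the size of an error that would occur only if someone did so. That caveat stands. But the integration step is not written down, and section 5.4 names its outcome explicitly.

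A reader might also infer that the bootstrap is unadjusted. The document does not say so. The adjusted estimation is described just before it, and repeating that estimation in each resample is a fair reading. The widths in step 4 apply only on the unadjusted reading and at assumed correlations. Even then the trial would not fall below its design, since the stated power already rests on an unadjusted SD; it would forgo a gain.

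Two further complaints are tempting and do not hold. The conditional surgeon effect is a prespecified fallback for a variance estimated at zero, which is sensible. And an exploratory subgroup model does not have to contain the primary model as a special case.

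**Conclusion.** The point holds as a defect of specification in a primary analysis. Section 5.4 as written does not regress its own endpoint, it disagrees with section 5.5 on the dependent variable, and it leaves open whether the bootstrap interval belongs to the adjusted estimate. This follows from the text and needs no numerical assumption.

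The sizes are conditional. The factor of about 2 assumes a roughly constant utility difference and matters only if the coefficient is read as QALYs. The 5% to 15% in interval width assumes an unadjusted bootstrap and r of 0.3 to 0.5. The omission of planned procedure is secondary: no bias, and about 2 to 3 points of power at most if procedure explains up to 10% of QALY variance. The planned sample size and its stated power are not in question.

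**What to change.** Rewrite the primary QALY analysis in section 5.4 as one model and one interval:

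- Outcome: each patient's 24-month QALY, as section 5.4 already defines it.
- Fixed effects: treatment group, baseline EQ-5D utility and planned procedure. Random effect: surgeon, with the existing fallback if the variance component is not positive.
- Primary estimate: the treatment coefficient of this model, in QALYs.
- Interval: refit the same model, with the same fallback, in every bootstrap sample and take the percentiles of the treatment coefficient.
- Missing and censored utilities: keep the rules in sections 2.3, 5.4 and 5.4.1 (zero after death, multiple imputation, inverse weighting for censored patients). State how they feed into this model and in what order imputation or weighting and resampling are done.
- Keep comparisons of utility at each visit as descriptive, and word the model check for a single QALY outcome per patient.

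The cost is a change of wording, a few degrees of freedom for procedure and some extra computing. No new data are needed and the sample size does not change.
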